1.1.3 Estimand

The estimand of the primary objective is defined by the following 5 attributes:

- Treatment: Single dose of AT132
- Population: Male participants with ventilator-dependent XLMTM, as defined by the inclusion/exclusion criteria of the study
- Endpoint: Change from baseline in hours per day of ventilation support at Week 24
- Intercurrent events and their corresponding strategies: For study discontinuation due to death or due to lack of efficacy, a composite strategy will be adopted, where participants with the intercurrent event before Week 24 having missing observation(s) after the intercurrent event will have those missing observations(s) imputed by unfavorable values ([Appendix 2](#))
- Population level summary: Mean change from baseline, by AT132 dose level

The estimand framework described above will be applied to all relevant primary and secondary efficacy endpoints.

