The change from baseline will be analyzed using the MMRM in a similar method to that used for the primary analysis of the primary efficacy endpoint, described in [Section 4.3.2](#).

Estimated change from baseline in MIP at Week 24 will be summarized by dose level.

In addition, the MIP and corresponding change from baseline at each visit will be summarized descriptively by dose level group.

If a subject has discontinued the use of the ventilator and has 2 assessments with the MIP at 80 cmH₂O, testing for MIP, MEP, and P0.1 will not be required for future visits.

Subject line plots of the MIP over time by will be created.

4.4.2.2.4 Change from baseline in quantitative analysis of myotubularin expression in the muscle biopsy at Week 24

The change from baseline will be analyzed using the MMRM in a similar method to that used for the primary analysis of the primary efficacy endpoint, described in [Section 4.3.2](#).

Estimated change from baseline in myotubularin expression levels at Week 24 will be summarized descriptively by dose level.

In addition, the myotubularin expression levels and corresponding change from baseline at each visit will be summarized descriptively by dose level group.

Subject line plots of the muotubularin expression levels over time will be created.

These data will also be listed.

4.4.2.2.5 Change from baseline in quality of life assessments at Week 24 (ie, the Assessment of Caregiver Experience with Neuromuscular Disease [ACEND] and Pediatric Quality of Life Inventory [PedsQL])

The change from baseline will be analyzed using the MMRM in a similar method to that used for the primary analysis of the primary efficacy endpoint, described in [Section 4.3.2](#).

Estimaged change from baseline in the ACEND and PedsQL scores (described below) at Week 24 will be summarized descriptively by dose level.

In addition, the ACEND and PedsQL scores and corresponding change from baseline at each visit will be summarized descriptively by dose level group.

Subject line plots of the ACEND and PedsQL scores over time will be created.

ACEND

The ACEND was developed to measure impact on the lives of parents/legally authorized representatives (LARs)/caregivers caring for children with severe neuromuscular disorders ([Matsumoto, 2011](#)). Several domains of the ACEND (time, finance, and emotion) are relevant to assessing the caregiver burden of the parents of children with XLMTM.

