ACEND contains 41 items which reflect 2 domains (physical impact and general caregiver impact). The physical impact domain includes 4 sub-domains: feeding/grooming/dressing (6 items), sitting/play (5 items), transfers (5 items) and mobility (7 items). The general caregiver impact domain includes 3 sub-domains: time (4 items), emotion (9 items), and finance (5 items). Score for each item is based on the 6- or 5-point ordinal scale, and scores for each domain and subdomain are scored on a scale of 0 - 100. Higher scores reflect

caregivers experiencing less intense care-giving impact. Sub-domain and total scores are thus meant to confer “impact health” in each caregiver respondent (Xu, 2020).

Raw scores for each subdomain are created by computing the algebraic mean of the items for those respondents who completed one item or more; setting missing for those items with no responses. Then, the arithmetic mean of the responded items is standardized to a 0 to 100 score using the following formula:

$$100 * \frac{\text{arithmetic mean of the items in subdomain} - 1}{\text{maximum item score in the subdomain} - 1}$$

Transformed scores should be 0 to 100 for each subdomain.

A total score can be calculated as the mean of the 7 subdomain scores. Domain scores will be calculated as the mean of the sub-domains. When any subdomain scores are missing, the total score (or domain score) will be missing. No items, subdomain scores, domain score, or total scores will be imputed.

Total scores and corresponding change from baseline will each be analyzed by MMRM as described above at Week 24 and summarized descriptively by dose level group and visit.

PedsQL

The PedsQL is a tool designed to measure health-related quality of life in healthy children and adolescents and those with acute and chronic health conditions. The PedsQL measures the core dimensions of health as delineated by the World Health Organization, as well as role (school) functioning. This questionnaire has different modules that are administered depending on the age and condition of the child.

The PedsQL neuromuscular module was designed to measure health-related quality of life dimensions specific to children aged 2-18 years with neuromuscular disorders and has been validated in other neuromuscular disorders such as SMA (Iannaccone, 2009). This is the module of the questionnaire that is used in this study, and is considered suitable to be used for children < 2 years of age.

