5.2 Appendix 2 Unfavorable Values for Efficacy Estimand Imputation

Endpoint	Variable	Imputed value after ICE occurrence through Week 48
Primary	Hours of ventilation support	24 hours
Key Secondary	Achieving functionally independent sitting for at least 30 seconds	No (0)
Secondary	CHOP INTEND Total Score	0
	MIP	0
	Myotubularin expression	0
	ACEND total score	0
	PedsQL Scale	0
	PedsQL Summary Score	0
	Number of age-appropriate gross motor function milestones achieved	0
	Full ventilator independence achieved	No

ICE = intercurrent event

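### SAP 4.4.2.2.5 bars imputing ACEND total scores, Appendix 2 sets them to 0 after discontinuation due to death or lack of efficacy, and no sentence says which rule prevails

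*SAP*

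**What the plan says.** **The scoring section.** SAP 4.4.2.2.5 builds the ACEND total as the mean of seven subdomain scores, each on a 0 to 100 scale. Higher scores mean "caregivers experiencing less intense care-giving impact", so 0 is the worst possible value. On incomplete data it says "When any subdomain scores are missing, the total score (or domain score) will be missing", and then "No items, subdomain scores, domain score, or total scores will be imputed". The change from baseline is to be "analyzed using the MMRM in a similar method to that used for the primary analysis of the primary efficacy endpoint", with a cross-reference to Section 4.3.2. ACEND is also summarized descriptively by visit and dose level.

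**The estimand.** SAP 1.1.3 states: "For study discontinuation due to death or due to lack of efficacy, a composite strategy will be adopted". Observations missing after an event before Week 24 are replaced by unfavorable values. The section adds: "The estimand framework described above will be applied to all relevant primary and secondary efficacy endpoints".

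**The value to use.** Appendix 2 has a row for "ACEND total score" with the value 0, in a column headed "Imputed value after ICE occurrence through Week 48".

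**The model section.** SAP 4.3.2, to which ACEND is sent, carries its own statement that values missing after such an event before Week 24 are set to the unfavorable value (24 hours, for the primary endpoint).

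**The concern.** The two instructions concern the same variable, the ACEND total, and cannot both be obeyed for a child who dies or discontinues for lack of efficacy before Week 24. The scoring section leaves the later totals missing; Appendix 2 makes them 0.

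The choice changes the question answered. With the zeros, the Week 24 estimate follows the composite strategy, in which death or failure counts as the worst outcome. Without them, the MMRM treats later values as missing at random. It then estimates a change as though the child had gone on like comparable children still under observation. In the by-visit summaries the child is simply absent after the event. ACEND would then answer a different question from the one Section 1.1.3 sets for the secondary endpoints, and the report would not show it unless the choice were stated.

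**Working it through.** The plan states no ACEND figure, so there is nothing to reproduce. The check has three parts.

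**1. Do the texts conflict, and is there a tie-break?**

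| Source in the SAP | ACEND total after the event |
|---|---|
| 4.4.2.2.5, scoring rules | Not imputed; no exception named |
| Appendix 2 | Set to 0 |
| 1.1.3 | Composite strategy applies to relevant secondary endpoints |
| 4.4.2.2.5, analysis paragraph, with 4.3.2 | MMRM similar to the primary; 4.3.2 includes the unfavorable-value rule |
| Version history, v4.0 | Appendix 2 was edited: one ventilator row removed, column header changed to Week 48; the ACEND row remains |

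Three sources besides Appendix 2 point towards the zeros. None of them refers to the ban or limits it.

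**2. Direction.** Let n be the treated children in a dose group, d those with the event before Week 24, and f = d/n. Let B be the mean baseline, taken as equal for children with and without the event, and D the mean change in the others.

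- Scoring rule, descriptive Week 24 mean change: D.
- Appendix 2: each child with the event contributes 0 − B, so the mean is [(n − d)D − dB]/n = D − f(B + D).
- Difference: f(B + D).

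B + D is the mean Week 24 score of the other children, which cannot be negative. Leaving the zeros out therefore cannot lower the mean score. For the mean change, the same holds under the equal-baseline assumption. With unequal baselines it holds unless the others worsened by more than the baseline of those with the event.

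**3. Size.** Inputs from the documents:

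- Fatal outcomes: 1 at the low dose and 3 at the high dose (Protocol 1.5). No dates of death are given.
- High-dose n = 17 at the 08 July 2020 cutoff (Protocol 1.4.2).
- Low-dose n is not stated. It is inferred as 6 dosed (Protocol 1.4.2) + 3 controls awaiting dosing (Protocol 3.1) − 2 never dosed (SAP 1.3) = 7, if no replacement was enrolled.

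The documents give no ACEND values. Assumed ranges: B from 20 to 60, D from 0 to 20. So B + D runs from 20 to 80.

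| Dose group | Events before Week 24 | f | f(B + D), points |
|---|---|---|---|
| Either | 0 | 0 | 0 |
| Low (n = 7, inferred) | 1 | 1/7 | 2.9 to 11.4 |
| High (n = 17) | 1 | 1/17 | 1.2 to 4.7 |
| High | 2 | 2/17 | 2.4 to 9.4 |
| High | 3 | 3/17 | 3.5 to 14.1 |

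Example: high dose, d = 3, B = 40, D = 10. The difference is (3/17) × 50 = 8.8 points. The mean change is 10.0 under the scoring rule and 10.0 − 8.8 = 1.2 under Appendix 2.

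These figures are exact only for the Week 24 descriptive mean with equal baselines. The protocol schedules ACEND at baseline and Weeks 1, 2, 4, 12, 16 and 24 (Protocol 5.4 and 5.5). A child with scores before the event therefore still informs the MMRM, and a decline before the event would pull the estimate down. For the MMRM, f(B + D) is an approximation.

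**The case against.** The best reply is that the intended rule can be recovered. The ban is the last line of a questionnaire-scoring algorithm, after rules on unanswered items and missing subdomains, so it is naturally read as covering questionnaire non-response. The section then sends the totals to the 4.3.2 method, which contains the unfavorable-value rule. Section 1.1.3 reaches secondary endpoints, Appendix 2 names this variable, and the v4.0 edit left its row in place. The PedsQL rules likewise say a scale is not computed when more than half its items are missing, which would be so at any visit after death. That suggests scoring rules and intercurrent-event rules work at different levels.

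Most of this stands, and Appendix 2 is the likelier intent. It does not remove the conflict. The preceding sentence already makes the total missing when a subdomain is missing; the next one goes further and bars imputing the total itself, the variable that Appendix 2 imputes.

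Three stronger readings are tempting and not supported:

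- *Children who died are dropped from the endpoint.* Not from the MMRM if they had a post-dose ACEND score; only their later values are lost. They are absent from by-visit summaries after the event.
- *Benefit is overstated.* This is conditional on the scoring sentence being followed and on an event before Week 24. The documents do not say the scoring sentence wins, and they date no death.
- *ACEND is the only endpoint exposed.* The PedsQL scoring text, read just as literally, raises a similar question.

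**Conclusion.** The contradiction is in the current SAP text and should be resolved. Following the scoring sentence literally would depart from the stated composite estimand for both intercurrent events, death and discontinuation due to lack of efficacy. The departure is neutral or favourable to the reported result, subject to the baseline condition above.

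Its size cannot be fixed from the documents. For the Week 24 descriptive mean it runs from nil to about 14 points over the assumed ranges. The upper end needs all three high-dose deaths before Week 24, a baseline of 60 and a gain of 20. The ACEND values and the timing of death are assumptions, and the low-dose denominator is an inference.

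Severity is low. ACEND is one of several other secondary endpoints, SAP Section 2 rules out hypothesis testing, and results are described by dose level.

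**What to change.** Replace the sentence in SAP 4.4.2.2.5 with: *Except for values after an intercurrent event (Section 1.1.3), which are set per Appendix 2, no items, subdomain, domain or total scores will be imputed.* In the same section, state whether the by-visit ACEND summaries include those zeros.

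The cost is two sentences of SAP wording, with no new data. It should be done before database lock. The drawback is that the reported ACEND change may be less favourable, possibly markedly so if deaths fell before Week 24.

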3.0	10-Jan-2024	Demographic and Other Baseline Characteristics (4.2.4)	Demographic summaries updated to include one for randomized participants for CT.gov reporting purposes. In addition, baseline characteristics updated to include only the relevant ones with corresponding data able to be summarized. Removed bar chart of medical history.	Aligning SAP to protocol Amendment version 11.0; CT.gov reporting requirements. Bar chart removed due to being extraneous.

SAP Version	Approval Date	SAP Section(s)	Change	Rationale
3.0	10-Jan-2024	Glucocorticoid Administration (4.2.6)	Summary updated to remove summary statistics of total dose administered. Details added regarding presentation of data related to taper.	Analysis aligned to what data is considered relevant.
3.0	10-Jan-2024	Extent of Exposure (4.2.7)	Summary of duration on study added.	Requested by clinical team.
3.0	10-Jan-2024	Primary Endpoint Analysis (4.3), Secondary Endpoint Analysis (4.4), Exploratory Endpoint Analysis (4.5)	Definition of baseline updated for primary analysis. Hypothesis testing removed. All analyses updated to align with Protocol Version 11.0 endpoints. Sensitivity analysis updated. Clarification added for motor milestones missing data imputation logic for protocol V1.0 - 4.0.	Aligning SAP to protocol Amendment version 11.0
3.0	10-Jan-2024	Main Analytical Approach	Choice of covariance structures if the unstructured structure doesn't converge has been updated. All comparisons and hypothesis testing has been removed from the primary analysis. MMRM results will only be presented for the change from baseline Week 24 time-point. Analysis dataset for analysis has been updated to FAS. Removal of continuous baseline values (e.g., age, ventilator status and duration, as well as baseline values for CHOP-INTEND, MIP and MFM20/32) being used as covariates in the MMRM.	Aligning SAP to protocol Amendment version 11.0; simplifying the model structure.
3.0	10-Jan-2024	Definition of Key Secondary Endpoint (4.4.1.1)	Removed logic for deriving missing motor developmental milestones. Due to the changes of objective of V 11.0 of the protocol, simple descriptive statistics of only available results were considered sufficient for the purpose.	Simplifying the analysis given the descriptive nature of the study.

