4 STATISTICAL ANALYSES

4.1 General Considerations

The study is no longer able to address the stated objectives, hence the statistical analysis will provide descriptive summaries by treatment groups.

Continuous data will be summarized descriptively including the number of participants (n), mean, standard deviation (SD), median, minimum and maximum. Categorical data will be summarized by frequencies and percentages. Percentages by categories will be based on the number of participants with no missing data, i.e. the percentages for the non-missing categories will add up to 100%.

All data summarization and analyses will be performed using SAS® Version 9.4 or higher on Red Hat Enterprise Linux. Specifications for table, figures, and data listing formats can be found in the TLF specifications.

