4.4 Secondary Endpoints Analysis

4.4.1 Key Secondary Endpoint

4.4.1.1 Definition of Endpoint

Percentage of participants achieving functionally independent sitting for at least 30 seconds by Week 24.

The primary source of data is the motor milestone eCRF. However, if that data isn't available for the visit, then Bayley III item #26 will be used to determine whether the participant achieves (Yes) or doesn't achieve (No) the milestone.

If both the motor milestone or the Bayley result are not available, but the participant attended the visit, then their result will be included in the summary as "missing".

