Each item of the questionnaire is measured on a 5-point likert scale from – 0 (Never) to 4 (Almost always). The module is composed of 25 items comprising 3 dimensions:

- About My Neuromuscular Disease (17 items)
- Communication (3 items)
- About Our Family Resources (5 items)
- Total Scale Score

Higher scales/scores indicate lower problems.

Scores are derived in the following way:

- Step 1: Transform Score

- Items are reversed scored and linearly transformed to a 0-100 scale as follows: 0=100, 1=75, 2=50, 3=25, 4=0.
- Step 2: Calculate Scores by Dimensions x
 - If more than 50% of the items in the scale are missing, the scale scores should not be computed, $x \text{ Mean score} = \frac{\text{Sum of the items}}{\text{number of items answered}}$.
 - If more than 50% of the items in the scale are missing, the Scale Scores should not be computed.
 - If 50% or more items are completed: Impute the mean of the completed items in a scale.
- Total Score: Sum of all the items over the number of items answered on all the Scales.

Per protocol, the parent-report version of the questionnaire is supposed to be administered. In the case that the child-report version of the questionnaire is administered, the scoring algorithm will be adjusted accordingly.

Total scores and corresponding change from baseline will each be analyzed by MMRM at Week 24 as described above and summarized descriptively by dose level group and visit.

4.4.2.2.6 Number (%) of age-appropriate clinically relevant gross motor function milestones attained through Week 24

Protocol versions 1 to 4:

Bayley and motor milestone collection was intermittent and not required in versions 1 – 4 of the protocol, so data may be missing for some participants at some visits. In addition, the motor milestone eCRF was not added until version 5.0 of the protocol. As such, the Bayley III item (referenced in [Table 1](#)) corresponding to each motor milestone will be used for the analysis of the motor milestone data collected under protocol version 1 – 4. If the Bayley III result is not available for the visit, but the participant attended the visit, then their result will be included in the summary as “missing”.

Protocol versions 5+:

The motor developmental milestones listed in [Table 1](#) below will be derived in form of Yes (achieved) and No (not achieved).

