 - 2a. Identify the age of the child in months to determine the “start point” item

Age	Start Point	Item Number
16 days – 1 month 15 days	A	1
1 month 16 days – 2 months 15 days	B	1
2 months 16 days – 3 months 15 days	C	5
3 months 16 days – 4 months 15 days	D	9
4 months 16 days – 5 months 15 days	E	9
5 months 16 days – 6 months 15 days	F	15
6 months 16 days – 8 months 30 days	G	19
9 months 0 days – 10 months 30 days	H	22
11 months 0 days – 13 months 15 days	I	35
13 months 16 days – 16 months 15 days	J	39
16 months 16 days – 19 months 15 days	K	42
19 months 16 days – 22 months 15 days	L	45
22 months 16 days – 25 months 15 days	M	48
25 months 16 days – 28 months 15 days	N	48
28 months 16 days – 32 months 30 days	O	51
33 months 0 days – 38 months 30 days	P	54
39 months 0 days – 42 months 15 days	Q	57

- 2b. If the child has three consecutive scores of 1 beginning with their ‘start point’ item, then this is the Basal aka “floor”.
- 2c. Otherwise, if any of the first 3 questions of the ‘start point’ are scored as 0, moving backwards towards 1, find the first instance prior to the initial start point where there are 3 consecutive questions with the score of 1. The first of these 3 will be the new “Basal”.
- 2d. If there are no instances of 3 consecutive scores of 1 occurring before the initial ‘start point’, then the “Basal” will be item 1 regardless of how the child scored on questions 1, 2 and 3.
3. Establish the “Ceiling”: the first time score of 0 appears on five consecutive items.
4. Count the number of items for which the child receives credit: “Basal” to “Ceiling”. Anything after the “ceiling” value is considered as score 0 regardless of what’s entered.
5. Count the number of items preceding the “Basal”. Usually these will be un-administered, but there are instances where these questions have been administered despite the later ‘start point’. Regardless of whether they are administered or un-administered, all the scores prior to the “Basal” should be counted as receiving credit (1).
6. Sum the numbers from step 4 and 5 to receive the raw score.

4.5.1.2.4 Change from baseline in total raw score in the fine motor domain of the Bayley-III at Week 24

The raw Bayley-III fine motor domain scores and corresponding change from baseline at each visit will be summarized descriptively by dose level group.

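### Milestones read from single Bayley-III items have no rule for items the test skips, so pre-v5 sitting and milestone percentages can be misstated

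*SAP*

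**What the plan says.** SAP 4.4.2.2.6 explains that Bayley and milestone collection was intermittent under protocol versions 1 to 4 and that "the motor milestone eCRF was not added until version 5.0 of the protocol". The Bayley-III item "corresponding to each motor milestone will be used for the analysis of the motor milestone data collected under protocol version 1 – 4". For a gap, the result is shown as missing; the rule reads: "If the Bayley III result is not available for the visit, but the participant attended the visit, then their result will be included in the" …

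For the key secondary endpoint, SAP 4.4.1.1 takes the milestone eCRF first; failing that, "then Bayley III item #26 will be used to determine whether the participant achieves" sitting. If neither source is available at an attended visit, the result is again shown as missing.

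SAP 4.5.1.2.3 sets out how the same gross motor test is scored. Testing starts at an age-based item, items before the basal are usually not administered, and the ceiling is the first run of five zeros. On the items before the basal it says: "Regardless of whether they are administered or un-administered, all the scores prior to the" basal count as credit. Everything after the ceiling counts as 0.

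The SAP version history for v3.0, under the key secondary endpoint, records: "Removed logic for deriving missing motor developmental milestones". The reason given is that descriptive statistics of available results were enough.

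Two denominators are in play. SAP 4.1 says: "Percentages by categories will be based on the number of participants with no missing data". SAP 4.4.2.2.6 uses every participant who attended and is old enough for the milestone, so a missing result stays in the denominator.

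**The concern.** An item that was not administered because the child started above it, or stopped before it, is not uninformative. The SAP's own scoring treats the first as passed and the second as failed. The milestone sections give neither a value. Taken with the removal of the derivation logic, the natural reading is that both become missing.

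That missingness depends on the outcome. Able children lose milestones they have passed, and weak children lose failures. In a study with no hypothesis testing, these percentages are themselves the result, and the low-dose group is small enough for one child to move them visibly.

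**Working it through.** The documents give no Week 24 sitting or milestone percentage, so there is no planned figure to reproduce. The check has four steps.

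**1. Which milestone items lie below the start item.** Inputs: the gross motor start-point table (SAP 4.5.1.2.3) and the nine Bayley items in SAP Table 1 (9, 20, 26, 33, 34, 35, 37, 40, 42). If the basal is set at the start item, the items skipped are:

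| Age from | Start item | Milestone items below it |
|---|---|---|
| 5 months 16 days | 15 | 9 |
| 9 months 0 days | 22 | 9, 20 |
| 11 months 0 days | 35 | 9, 20, 26, 33, 34 |
| 13 months 16 days | 39 | those, plus 35, 37 |
| 16 months 16 days | 42 | those, plus 40 |
| 19 months 16 days | 45 | all nine |

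**2. Effect on one child's count.** Expected ages are from SAP Table 1. Only age-expected milestones are counted, and the child passes the first three items from the start.

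- 12 months, items 35 to 37 passed: 1 of 6 expected milestones as recorded; 5 of 6 with basal credit.
- 14 months, items 39 to 41 passed: 0 of 8 as recorded; 7 of 8 with basal credit.
- 20 months, items 45 to 47 passed: 0 of 10 as recorded; 9 of 10 with basal credit. The raw score for the same visit is at least 47.

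The one milestone still absent each time is the 10-second sit. It has no Bayley item in Table 1, yet it enters the expected count from 9.2 months. Under the v1-4 rule as written, no child past that age can reach the category of all expected milestones.

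**3. Effect on a group percentage.** Let k of n children truly sit.

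- One skipped pass, missing excluded: (k-1)/(n-1), which is below k/n whenever k < n. Missing kept: (k-1)/n.
- One skipped failure, missing excluded: k/(n-1), which is above k/n. Missing kept: k/n, no change.

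With n = 7 and an assumed k = 4 (4/7 = 57.1%):

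| | Missing excluded (SAP 4.1) | Missing kept (SAP 4.4.2.2.6) |
|---|---|---|
| One skipped pass | 3/6 = 50.0% | 3/7 = 42.9% |
| One skipped failure | 4/6 = 66.7% | 4/7 = 57.1% |

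**4. Who is exposed.** Protocol 1.4.2 says all six low-dose children were at least 2 years past dosing at the 08 July 2020 cutoff, so the latest dosing date is 08 July 2018. Counting that as Day 1, Day 168 falls on 22 December 2018. Day 210, the end of the Week 24 window for milestones and Bayley in SAP Table 9, falls on 02 February 2019. Protocol v5 is dated 01 May 2019. All six therefore rely on Bayley items at Week 24.

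Low-dose n: 6, plus 1 of the 3 controls still undosed at v8/v9, since SAP 1.3 says two were never dosed; this assumes no replacement was enrolled. The exposed share is 6/7 = 86%.

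High-dose n is 17 (Protocol 1.4.2). Cohort 2 had 3 initial children plus 3 to 5 more, and its Week 24 data informed the v5 dose decision. Assuming 3 to 8 reached Week 24 before v5, the share is 3/17 = 18% to 8/17 = 47%. The exact number is not given.

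**The case against.** The strongest reply is that the SAP never says a skipped item is missing. The rule follows a sentence about intermittent collection, and the unavailable result could mean the whole test. The v3.0 history also records a clarification of missing-data logic for v1-4 milestones, and 4.4.2.2.6 refers to flowchart logic. This stands in part. But if the whole test is meant, a skipped item has no rule at all. No flowchart appears in the text reviewed; if the full SAP contains one that covers skipped items, that part of the point is answered.

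Next, the basal and ceiling conventions belong to a raw score and can override an observed item, so carrying them over is a choice. That is fair. It is why a recorded score should take precedence and inferred values should be flagged.

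Third, both routes are narrower than they first look. A non-sitter aged 11 months or more who fails the start items is tested backwards to three consecutive passes, which will usually record item 26. The ceiling route at Week 24 therefore mainly needs a child under 11 months, dosed before about 5.5 months of age (11 months less 168 days). In the other direction, an endpoint met by Week 24 may let an earlier visit count, and five of the six low-dose children did not sit at baseline. Both points stand as limits on size. They are incomplete: Protocol Section 2 words the endpoint as at Week 24, early Bayley collection was intermittent, and the by-visit tables get no help from earlier visits.

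A reader might go further and infer that the percentages are wrong, and mainly in the low-dose group. The documents do not support that. They give no item-level data or ages, SAP 4.5.1.2.3 notes that some pre-basal items were administered anyway, and by head count the exposure may be similar in the two dose groups.

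**Conclusion.** The gap is real and, followed as written, can produce a wrong result as well as leave a term undefined. Below-basal skips can understate sitting and milestone attainment under either denominator. Above-ceiling skips can inflate the sitting percentage only if missing values are excluded; they leave the attended-and-age-eligible percentages unchanged.

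The number of records affected is unknown, from none to all v1-4 records. The illustrated shifts for one child out of seven are 7.1 points (57.1% to 50.0%) and 14.3 points (57.1% to 42.9%) down, or 9.5 points (57.1% to 66.7%) up. They rest on an assumed four sitters, on sites having followed the start and stop rules, and on a derived low-dose n of 7. The exposed share is larger in the low-dose group, but high-dose Cohort 2 children are exposed as well. Severity is moderate: the primary endpoint is untouched and all summaries are descriptive.

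**What to change.** In SAP 4.4.1.1 and 4.4.2.2.6, for any milestone taken from Bayley-III at a visit:

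- item administered: use the recorded score;
- item not administered and below that visit's basal: Yes;
- item not administered and above that visit's ceiling: No;
- missing only if no gross motor Bayley was done at the visit.

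Flag inferred values in the listing. In the same edit:

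- name one denominator rule for sitting, either SAP 4.1 or the attended-and-age-eligible rule;
- replace the flowchart reference in 4.4.2.2.6 with the rule above;
- state how the 10-second sit is derived for v1-4 data, or exclude it from the expected count there. A 30-second Yes implies a 10-second Yes, but a 30-second No settles nothing.

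The cost is SAP wording and a few lines of code that reuse the basal and ceiling already planned for the raw score. The small downside is that some Yes and No values are inferred from the test's rules, not observed.
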